2 INTRODUCTION

2.1 Purpose of Trial

ASN51 is a reversible and substrate competitive inhibitor of O-linked N-acetylglucosaminidase (O-GlcNAcase; OGA), which is in clinical development for the treatment of AD caused by intracellular brain proteinopathies.

In patients with AD, the formation of neurofibrillary tangles (NFTs) consisting of the protein tau is tightly linked to the onset and progression of dementia symptoms (La Joie, Visani et al. 2020). Inhibition of the OGA enzyme with ASN51 stabilizes a post-translational carbohydrate modification of tau called O-GlcNAc by preventing its removal. Increasing the level of O-GlcNAc modification of tau is hypothesized to prevent the aggregation of tau into toxic paired helical filaments that deposit as NFTs in the brains of patients with AD. Orally administered OGA inhibitors have been shown to slow the development of NFT pathology in preclinical models of early AD by up to 80% in some brain regions and represent a promising new disease-modifying treatment approach (Yuzwa, Shan et al. 2012, Graham, Gray et al. 2014, Yuzwa, Shan et al. 2014, Hastings, Wang et al. 2017, Wang, Smith et al. 2018, Wang, Li et al. 2020, Permanne, Sand et al. 2022, Pratt and Vocadlo 2023, Rostgaard, Jul et al. 2023, Mergott 2024, Nery 2024).

ASN51 has been administered to healthy volunteers in multiple Phase 1 clinical trials to date and has been deemed suitable for chronic dosing in this Phase 2 study of early AD based on available nonclinical and clinical data as described in the Investigator's Brochure (IB).

The purpose of the ASN51-201 trial is to evaluate the safety, pharmacokinetics (PK), effect on biomarkers of disease pathophysiology and pathology, and preliminary effects on measures of clinical efficacy of multiple doses of ASN51 in adults with early, symptomatic AD.

[figure not shown]
2.2 Summary of Benefits and Risks

[figure not shown]

2.2.2 Risk Summary

2.2.2.1 Intervention Risks and Mitigation

2.2.3 Overall Benefit: Risk Conclusion

3 OBJECTIVES AND ENDPOINTS

Objectives	Endpoints							
Primary								
To evaluate the safety and tolerability of daily doses of ASN51 as compared with placebo	Incidence and severity of AEs Changes from baseline in laboratory safety assessments (including clinical chemistry, hematology, urinalysis, and serum hormone markers), Changes from baseline in vital signs, 12-lead electrocardiograms, and physical (including neurological) examinations Changes from baseline in C-SSRS							
Key Secondary								
To evaluate the effect of daily doses of ASN51 as compared with placebo on the pathophysiology of early AD To evaluate the effect of ASN51 versus placebo in change from Baseline to Week 24 on the pathophysiology of early AD	Change from baseline through Week 24 in CSF pTau217 Change from baseline through Week 24 in CSF total tau protein Change from baseline through Week 24 in plasma pTau217							
Other Secondary								
To evaluate the effect of daily doses of ASN51 as compared with placebo on tau pathology in early AD	Change from baseline through Week 24 in MK-6240 tau PET signal							
To evaluate the pharmacokinetics of ASN51 in early AD	Trough (C _{min}) at steady state and maximum (C _{max}) concentration of ASN51 in plasma at steady state through Week 24							
Tertiary/Exploratory								
To evaluate the effect of daily doses of ASN51 as compared with placebo on the pathophysiology of early AD To evaluate the effect of ASN51 versus placebo in change from Baseline to Week 24 on biomarkers of early AD	 Change from baseline through Week 24 in biomarkers, including but not limited to: Plasma Phosphorylated tau 181, GFAP, Aβ42/40, NFL CSF Phosphorylated tau 181, microtubule binding region tau 243, GFAP, Aβ42/40, NFL, neurogranin 							

ct of daily doses of with placebo on in early AD Change from baseline through Week 24 in: CDR-SB score ADAS-Cog13 score MMSE score ADCOMS score						
com Baseline to cructure Change from baseline through Week 24 in volumetric brain MRI parameters (e.g., whole brain volume, lateral ventricular volume, and cortical thickness measures of certain brain regions)						
Extension Period						
-term safety and 1 in early AD The incidence and severity of AEs over the DB placebo-controlled and LTE periods of the study						
-term efficacy of by clinical, litional assessments cipant and study partner Change over the placebo-controlled (from DB baseline) and long-term extension (from LTE baseline) periods of the study in: Disease-related biomarker levels in CSF, which will include, but are not limited to, amyloid and tau proteins (in a subset of participants) Disease-related biomarker levels in blood, which will include, but are not limited to, amyloid and tau proteins MK-6240 tau PET signal Whole brain volume, hippocampal volume, ventricular volume, and cortical gray matter volume measured by MRI CDR-SB score ADAS-Cog13 score MMSE score						
ADAS-Cog						

AD = Alzheimer's disease; ADAS-Cog13 score = Alzheimer's Disease Assessment Scale – Cognitive Behavior Subscale 13; ADCOMS = Alzheimer's disease composite score; AE = adverse event; CDR-SB = Clinical Dementia Rating – Sum of Boxes; CSF = cerebrospinal fluid; C-SSRS = Columbia-Suicide Severity Rating Scale; DB = double-blind; GFAP = glial fibrillary acidic protein; LTE = Long-term Extension; MMSE = Mini-Mental State Examination; MRI = magnetic resonance imaging; NFL = neurofilament light chain; PET = positron emission tomography.

4 TRIAL DESIGN

4.1 Description

ASN51-201 is a multi-site, placebo-controlled, double-blind, randomized, parallel group trial with a long-term extension (LTE). The purpose of the trial is to evaluate the safety, PK, effect on biomarkers of disease pathophysiology and pathology, and preliminary effects on measures of clinical efficacy of multiple doses of ASN51 in adults with early AD.

The trial design is depicted in Section 1.2.

Screening for eligibility will be conducted using a tiered approach and may be completed over multiple days. An abbreviated screening informed consent process may be utilized to conduct initial prescreening (i.e., denoted Tier 1 and Tier 2 per Table 1), if allowed at the investigative site. Participants who meet Tier 1 eligibility criteria, including MMSE, should proceed to Tier 2 (plasma pTau217). Tier 1 and Tier 2 assessments may take place on the same day.

Informed consent for the full trial must be obtained prior to performing any Tier 3 and Tier 4 screening procedures 2 per Table 1. Participants may proceed to Tier 4 only after all criteria from Tier 1, 2, and 3 have been met.

The duration of the Screening Period may be up to 8 weeks (may be extended on a case-by-case basis by the Sponsor Medial Monitor) to allow for the completion of assessments and for the evaluation of required laboratory, ECG, and imaging tests per the Schedule of Activities provided in Table 1.

Dose selection has been enabled by two Phase 1 target engagement trials that utilized an OGA enzyme PET ligand to define the precise relationship in human beings between plasma concentration and brain target occupancy. Further details on dose selection can be found in Section 6.2.

Eligible participants will be randomized in a 1:1:1 ratio to one of the following planned arms:

- ASN51: once daily by mouth
- ASN51: once daily by mouth
- Placebo once daily by mouth.

Eligible participants will self-administer ASN51 once daily at the assigned dose level during a 24-week Double-blind (DB) Intervention Period. The participant (accompanied by a designated study partner) will be asked to return to the investigative site approximately every 4 weeks over two days as long as all assessments are completed within the visit window.

[figure not shown]
Following completion of the DB Intervention Period, all participants will be offered continued ASN51 in the 36-week LTE Period. Participants initially randomized to placebo will receive ASN51 (randomized 1:1

ASN51 will continue at the assigned dose level, unless dose modification is recommended based on emerging data.

A safety Follow-up Visit will take place 4 weeks after the last dose of ASN51.

A Schedule of Activities for the DB Intervention Period and LTE Period are provided in Table 2 and Table 3, respectively.

4.2 Rationale for Trial Design

The 24-week DB Intervention Period of chronic administration of ASN51 in patients with early AD is appropriate to establish safety and tolerability of ASN51 at multiple dose levels as measured by changes in laboratory safety assessments (including clinical chemistry, hematology, urinalysis, and serum hormone markers), vital signs, 12-lead ECGs, Columbia-Suicide Severity Rating Scale (C-SSRS), and physical examinations (including neurological examination).

The 24-week DB Intervention Period is also of sufficient duration to perform a population PK analysis of trough (C_{min}) and peak (C_{max}) PK at steady-state, to observe initial changes in AD pathophysiology and pathology as measured by fluid biomarkers, and to observe initial changes in cognitive function as assessed by AD clinical outcome measures.

4.3 Start of Trial and End of Trial

The Start of the Trial is the estimated date on which the clinical trial will be open for recruitment of participants.

A participant will be considered enrolled in the trial once all screening procedures have been completed, the results evaluated by the Investigator to confirm eligibility, and the participant is randomized into the trial.

The end of the trial is defined as the date of the last protocol-specified visit for the last participant participating in the trial.

The Sponsor reserves the right to discontinue the trial at any time for any reason or discontinue participation of an investigator due to poor enrollment or noncompliance (Section 10.5).

5 POPULATION

5.1 Selection of Trial Population

This trial will be conducted in adults (aged 50 to 80 years) with a diagnosis of early AD. Eligible patients should meet diagnostic criteria for mild cognitive impairment (MCI) due to AD or mild AD dimentia, collectively referred to as early AD. All patients should have a plasma pTau217 concentration above a pre-determined cut-off to confirm the presence of brain amyloid pathology. Mini Mental Status Examination (MMSE) should range between ≥ 20 and ≤ 28 at baseline with a global Clinical Dementia Rating (CDR) score of 0.5 or 1.0. All participants should meet National Institute on Aging and the Alzheimer's Association (NIA-AA) diagnostic criteria for MCI or mild AD (Jack, Bennett et al. 2018) and have a CDR memory box score of 0.5 confirming episodic memory impairment.

5.2 Rationale for Trial Population

Early AD patients are expected to have tau pathology present at baseline, maximizing the probability of observing an anti-tau treatment effect with ASN51.

The Sponsor has taken reasonable measures to ensure the protection and safety of this population including specific criteria to exclude patients with significant cardiovascular or neurological conditions, or who require concomitant medications for conditions which may confound trial results. Additional criteria related to concomitant medications or abnormal coagulation parameters were included to mitigate risks associated with LP procedures. Considerations included comorbidities likely present in the selected population, and emerging safety data from Phase 1 clinical trials.

For Investigator questions regarding participant eligibility or clinical significance of abnormalities, discussion with the study Medical Monitor is strongly encouraged.

Individuals who do not meet criteria for trial eligibility must not be enrolled; there will be no protocol waivers or exemptions.

5.3 Inclusion Criteria

To be eligible to participate in this trial, an individual must meet all the following criteria:

- Male or female age 50 to 80 years inclusive at the time of consent.
- Ability of the participant and/or his/her legally authorized representative (e.g., parent, spouse, or legal guardian, where local regulations and institutional practices permit), as appropriate and applicable, to understand the purpose and risks of the study, to provide informed consent, and to authorize the use of confidential health information in accordance with national and local privacy regulations.

- Must consent to APOE genotyping. The participant's APOE status may be disclosed to him/her at the Investigator's discretion.
- 4. Must have a care partner who, in the Investigator's judgment, has frequent and sufficient contact with the participant (at least 10 hours/week) as to be able to provide accurate information about the participant's cognitive and functional abilities. The care partner must agree to accompany the participant to clinic visits and/or be available by telephone at designated times to provide information to the Investigator and study staff about the participant (and to attend in-person clinic visits that require care partner input for scale completion) and must agree to monitor the participant's administration of any prescribed medications. A care partner should be available for the duration of the study, and the participation of the same care partner for the duration of the study is a top priority. The care partner must be literate and provide informed consent.
- A plasma pTau217 result consistent with the presence of amyloid pathology (defined as > 0.18 pg/mL).
- A clinical diagnosis of AD at either the mild cognitive impairment or mild AD dementia stage per NIA-AA criteria (Jack, Bennett et al. 2018), consistent with Stage 3 and Stage 4 in the FDA draft guidance for early AD (FDA draft 2024).
- Gradual and progressive change in cognition for at least 6 months as reported by the participant and study partner.
- Global CDR of 0.5 to 1 (inclusive) and memory box score ≥ 0.5 at Screening.
- MMSE score of 20 to 28 (inclusive).
- Body mass index greater than 18.5 and less than 35 at Screening.
- 11. All men, regardless of fertility status, with non-pregnant women of childbearing potential partners must agree to at least one of the following contraception requirements from 28 days before baseline assessment through 90 days after last study drug administration:
 - a. Total abstinence: if in line with their preferred and usual lifestyle
 - b. Male sterilization by vasectomy with documentation of the procedure
 - c. Condom use
 - A highly effective method of contraception (Section 13.1.2) for the partner of a male participant.
- 12. Apart from a clinical diagnosis of MCI due to AD or mild AD dementia, the participant must be in good health as determined by the Investigator, based on medical history and screening assessments.

5.4 Exclusion Criteria

An individual who meets any of the following criteria will be excluded from participation in this trial:

5.4.1 Exclusion Criteria by Medical History

- Any medical or neurological/neurodegenerative condition (other than AD) that, in the
 opinion of the Investigator, might be a contributing cause to the participant's cognitive
 impairment (e.g., current history of substance abuse, uncontrolled vitamin B12 deficiency or
 abnormal thyroid function, stroke or other cerebrovascular condition, normal pressure
 hydrocephalus, Parkinson's disease, Lewy body dementia, cerebral amyloid angiopathy,
 frontotemporal dementia) or could lead to discontinuation, lack of compliance, interference
 with study assessments, or safety concerns.
- Non-amnestic presentation of AD as judged by the Investigator.
- Woman of childbearing potential (per CTFG 2020).
- Excessive alcohol use (defined as more than 3 alcoholic drinks per day or 21 drinks per week for men and 2 alcoholic drinks per day or 14 drinks per week for women) from the Screening Visit until the end of the Follow-up Period.
- History of cancer in the past 3 years. Exceptions: non-metastatic basal and/or squamous cell
 carcinoma of the skin, in situ cervical cancer, non-progressive prostate cancer, participants
 with cancer in remission > 5 years, or other cancers with low risk of recurrence or spread.
- History of human immunodeficiency virus infection (active or past), or active hepatitis C infection.
- 7. History of liver disease including hepatitis B, hepatitis C, primary biliary cholangitis, primary sclerosing cholangitis, alpha-1 antitrypsin disease, alcoholic liver disease, Wilson's disease, hemochromatosis, portal hypertension, biopsy-proven metabolic associated steatohepatitis, autoimmune hepatitis, drug induced liver disease.
- Clinically significant systemic infection or severe infection (e.g., pneumonia, septicemia) within the 30 days prior to Screening or between Screening and Day -1.
- History of seizures within 10 years prior to Screening Visit 1 or history of epilepsy (except for history of febrile seizures in childhood).
- 10. Presence of clinically significant and/or unstable psychiatric illness, in the Investigator's opinion (e.g., bipolar disorder), within the 6 months prior to Screening Visit 1 and/or a documented prior history of chronic schizophrenia.
- 11. History of major depressive disorder, bipolar disorder, or generalized anxiety disorder with an active episode in the past 5 years.

- History of diabetes mellitus. Participants with well-controlled diabetes mellitus and a hemoglobin A1c < 7% are permitted.
- Biotin supplementation ≥ 5,000 mcg/day from 28 days prior to Screening through the end of the Follow-up Period
- 14. History of bleeding disorder or predisposing conditions, blood clotting, or clinically significant abnormal results on coagulation profile at Screening, as determined by the Investigator.
- 15. Any major surgery within 12 weeks of Screening Visit 1 or during the screening period.
- 16. History of unstable angina, myocardial infarction, chronic heart failure (New York Heart Association Class III or IV), or clinically significant conduction abnormalities (e.g., unstable atrial fibrillation) within 1 year prior to Screening Visit 1.
- 17. Uncontrolled hypertension defined as an average of 3 systolic/diastolic blood pressure readings > 165 mmHg and/or > 100 mmHg, respectively, at Screening (blood pressure measurements exceeding these limits may be repeated as warranted by the Investigator, but values must be within the specified limits for the participant to be eligible for the study) or persistent systolic/diastolic blood pressure readings > 180/100 mmHg within 12 weeks prior to randomization (Study Day 1) that, in the opinion of the Investigator, are indicative of chronic uncontrolled hypertension.
- History of severe allergic or anaphylactic reactions.
- 19. Known or suspected history of drug or alcohol abuse within 2 years prior to Screening. Benzodiazepine and opioid use is permitted if in the clinical opinion of the Investigator the use is for an appropriate medical condition and not due to drug abuse.
- 20. Current serious or unstable illness, or any other condition that, in the judgement of the Investigator, would interfere with the ability to complete the study, pose significant risk to participant safety, or potentially confound interpretation of trial results.

5.4.2 Exclusion Criteria by Screening Assessments

- 21. Any clinically significant abnormality at screening in physical examination, vital signs, ECG, or laboratory test results that could place the participant at undue risk during the study, compromise the future interpretation of study assessments, or that suggests an alternative etiology for dementia other than AD.
- 22. At risk of suicide based on a "yes" response to the Columbia Suicide Severity Rating Scale (C-SSRS) suicidal ideation question 4 or 5 or any suicidal behavior assessment within 6 months before Screening, or has been hospitalized or treated for suicidal behavior within 5 years of Screening.

- Magnetic resonance imaging (MRI) evidence of vascular dementia or other findings suggestive of a major neurologic disorder other than AD.
- 24. Significant claustrophobia during MRI that, in the opinion of the Investigator, will prevent successful completion of required procedures.
- Heart rate > 100 beats per minute after 5 minutes of rest, without solicitation.
- 26. Confirmed demonstration of corrected QT interval using Fridericia's correction method (QTcF) of > 450 ms for males and > 460 ms for females (as read by the central reading facility).
- Median ECG (triplicate) PR interval > 200 msec at Screening.
- Positive hepatitis B virus surface antigen and/or hepatitis B e-antigen at Screening.
- Positive hepatitis C antibody test result at Screening.
- 30. Presence of bleeding disorder or abnormal coagulation parameters at Screening, including platelet count < 150,000 cells/ μ L or international normalized ratio (INR) > 1.5.
- 31. Estimated glomerular filtration rate < 60 mL/min/ 1.73 m 2 per Chronic Kidney Disease Epidemiology Collaboration at Screening.
- 32. Liver function, any of the following: ALT ≥ 1× the ULN, AST ≥ 1× ULN, total bilirubin level (TBL) ≥ 1× ULN, or alkaline phosphatase (ALP) ≥ 1× ULN at screening. Subjects with any degree of hepatic impairment as defined by the Child-Pugh classification are also excluded (e.g., classification B or C).

5.4.3 Exclusion Criteria by Concomitant Medications/Prior Therapies

- 33. Initiation or change in dose of an acetylcholinesterase inhibitor and/or memantine within less than 8 weeks prior to randomization.
- 34. Positive urine drug test at Screening. Testing positive for benzodiazepines or opioids in urine drug testing is permitted if determined by the Investigator to be due to appropriate medical use and not drug abuse. Medical cannabidiol (CBD) use is permitted if prescribed by a medical provider in accordance with local laws and if in the opinion of the Investigator its use does not pose a risk to participant safety or compromise a participant's performance on cognitive assessments.
- 35. Taking medications known to prolong PR or QT intervals (e.g., calcium channel blockers or beta blockers) unless on a stable dose of (or titrating) within 12 weeks prior to randomization.
- 36. Use of any medications that, in the opinion of the Investigator, may contribute to cognitive impairment, put the participant at higher risk for AEs, or impair the participant's ability to perform cognitive testing or complete study procedures.

- 37. Any prior or ongoing exposure to active or passive anti-amyloid immunotherapy, anti-tau immunotherapy, an anti-tau antisense oligonucleotide or gene therapy, or O-GlcNAcase inhibitor.
- 38. If previously exposed to an investigational product other than active or passive anti-amyloid immunotherapy, anti-tau immunotherapy, an anti-tau antisense oligonucleotide or gene therapy, or O-GlcNAcase inhibitor, then 12 weeks or 5 half-lives (whichever is longer) must have passed prior to randomization.
- Known allergy to any components of the ASN51 formulation.
- 40. Requires use of anticoagulants during trial participation (to permit safe CSF collection).
- 41. Prior use of a moderate or strong inhibitor of CYP3A4 within a period of 5 half-lives of randomization (refer to Appendix 16).
- 42. Prior use of a moderate or strong inhibitor of CYP2C19 within a period of 5 half-lives of randomization (refer to Appendix 16).

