6.6.2 Blinding and Unblinding

The initial 24 weeks of intervention will be administered in a double-blind fashion. Participants, Investigators, site personnel, and the Sponsor and/or designees will be blinded to randomization assignment.

The statistician(s) responsible for generating the randomization schedule, and personnel responsible for preparing trial intervention supplies will be unblinded.

Randomization numbers will be assigned sequentially. Each participant will be dispensed blinded trial intervention (ASN51 or placebo), labeled with the participant's unique randomization number. Unblinding mechanisms will be available by IWRS.

Should any trial stopping criteria (Section 7.4) be triggered the involved participant(s) will be unblinded to randomization assignment by the SRC to determine if the event was related to IMP.

In the event of an emergency, the Investigator has the sole responsibility for determining if unblinding of a participant's randomization assignment is warranted. The safety of the participant will be the first consideration in making such a determination. If a participant's randomization assignment is unblinded, the Sponsor Medical Monitor must be notified within 24 hours.

Following completion of the 24-week DB Intervention Period, data will be unblinded after database lock for the purpose of data analysis; however, participants, Investigators, and study site staff will remain blinded to DB treatment assignment until the end of the 36-week LTE Period (end of the study).

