If a clinically significant finding is identified (including changes from baseline in QTcF) after enrollment, the Investigator or qualified designee will determine if the participant may continue in the trial or if a change in participant management is required. Review of ECGs must be documented upon collection and any new clinically significant ECG finding should be reported as an AE. Central review of ECGs will also be performed (see Section 8.3.3.1).

Should the following events occur in an individual participant during the trial, the Investigator, in consultation with the Sponsor's Medical Monitor, will decide if study intervention should be interrupted or permanently discontinued:

- If a participant has median PR interval of 200 ms to 220 ms AND a change from baseline in PR interval of > 10% (triplicate measurements)
- If a participant has median PR interval > 220 ms (triplicate measurements).

Systemic Hypersensitivity Reactions

If the Investigator, after consultation with the Sponsor-designated Medical Monitor, determines that a systemic hypersensitivity reaction has occurred related to IMP administration, the participant should be discontinued.

Excluded Therapeutic Agent

If the participant requires treatment with an excluded therapeutic agent and temporary discontinuation cannot be met, IMP should be discontinued.

If a participant discontinues from the trial prematurely, reasonable efforts should be made to perform the Early Termination (ET) visit procedures as soon as possible, and schedule Follow-up Visit procedures 4 weeks after the last dose of ASN51.

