7.4 Trial Stopping Rules

Should any of following events occur, the SRC, Sponsor, and Coordinating Investigator (along with involved Investigator(s)) will convene on *ad hoc* basis (not to exceed 5 business days after knowledge of the event):

- Death of any participant within 28 days of receipt of IMP unless inextricably related to an alternative cause
- Two or more participants in a group show a 2nd degree AV block, or Mobitz type 2 confirmed with 2 consecutive ECGs, or 3rd degree AV block

- Hy's law is met for one participant, requiring all the following:
 - ALT or AST > 3 × ULN
 - o TBL > 2 × ULN
 - ALP < 2 × ULN
 - No other obvious reason for the liver injury, such as viral hepatitis, alcohol use, or another hepatotoxic drug
- AEs occurring in the same System Organ Class (SOC; irrespective of severity or seriousness) leading to discontinuation of trial intervention in 3 or more participants.

All available information regarding the event(s) will be evaluated. Based on reasonable clinical judgment, a decision will be made whether or not the event(s) needs to be further characterized with respect to progression and reversibility; and whether it is reasonable to alter ongoing treatment (criteria/monitoring), recommend a pause in further enrollment, or recommend stopping the trial.

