8.4.3.1 Drug Induced PR Prolongation

[figure not shown]
Drug-induced PR prolongation with Mobitz type 1 second degree AV block may be a risk associated with ASN51. TEAEs with the following Medical Dictionary for Regulatory Activities (MedDRA) Preferred Terms (PTs) will be considered an AESI for this trial:

[figure not shown]
 AV block first degree, AV block second degree Mobitz type I, AV block second degree Mobitz type II, and AV block third degree.

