9 STATISTICAL CONSIDERATIONS

A general description of the statistical methods planned to analyze the safety and preliminary efficacy of the IMP is outlined below. The analyses specified in this protocol will be expanded in the Statistical Analysis Plan (SAP) to include a detailed description of the analyses. The SAP will be finalized and approved prior to database lock.

Trial data will be reported using summary tables, figures, and data listings. Descriptive statistics will be used to summarize the data. For continuous variables, the mean, standard deviation, median, minimum, and maximum will be provided. For discrete data, incidence and percentages will be provided. Statistical tests will be 1-sided at the alpha level of 0.10, unless stated otherwise. P-values will be used descriptively and will have no inferential value. All p-values will be reported to the 3rd decimal place. Summary tables will include the data from the ASN51 groups combined, i.e., Placebo and ASN51 for the DB and LTE periods, respectively.

Baseline for all clinical laboratory evaluations, vital signs measurements, and 12-lead ECGs will be defined as the last evaluation before IMP administration. The timing of each protocol-specified assessment is provided in the Schedules of Activities (Section 1.3).

Two sets of analyses will be conducted. The first set of analyses will be conducted after all participants have had the opportunity to complete the Week 24 assessment or have discontinued the study (primary analysis Sections 9.1 through 9.7). The second set of analyses will be conducted when all participants have had the opportunity to complete the LTE or discontinued the study (Section 9.8).

For endpoints collected only once post-baseline, changes from baseline will be analyzed using an analysis of covariance (ANCOVA) model that includes the categorical effects of APOE4 status, use of AD medication, treatment group, and the continuous covariate of the baseline value of the variable being analyzed. The one-sided p-value (t-test on least squares means at Week 24) and two-sided 80%, and 90% confidence limits will be tabulated. The model will also include the randomization stratification factors (i.e., APOE4 status and use of AD medication).

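### Exclusion 35 admits participants who are still titrating a PR- or QT-prolonging drug, so its 12-week window does not secure a stable dose before the baseline ECG

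*Combined protocol and SAP*

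**What the plan says.** Exclusion 35 (Section 5.4.3) is aimed at people taking drugs that lengthen PR or QT, with calcium channel blockers and beta blockers as its examples. It excludes them "unless on a stable dose of (or titrating) within 12 weeks prior to randomization". Two items earlier, exclusion 33 treats symptomatic Alzheimer's drugs differently. There the excluded condition is "Initiation or change in dose of an acetylcholinesterase inhibitor and/or memantine within less than 8 weeks prior to randomization".

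The ECG matters in this trial for stated reasons. Section 8.4.3.1 says: "Drug-induced PR prolongation with Mobitz type 1 second degree AV block may be a risk associated with ASN51". It makes the AV-block preferred terms, from first to third degree, adverse events of special interest. Section 3 lists change from baseline in 12-lead ECGs among the primary endpoints. Section 9 fixes the reference point: baseline for "12-lead ECGs will be defined as the last evaluation before IMP administration".

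Two sets of PR limits apply. At entry, Section 5.4.2 excludes "Median ECG (triplicate) PR interval > 200 msec at Screening". After entry, Section 7.1.1 has two PR criteria. The first is "If a participant has median PR interval of 200 ms to 220 ms AND a change from baseline in PR interval of > 10" percent. The second is a median PR above 220 ms. Either one sends the decision to interrupt or stop treatment to the Investigator in consultation with the Medical Monitor.

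**The concern.** A stability window normally exists so that a background drug has settled before the reference measurement is taken. Here the words in brackets exempt the very people the window should hold back. Who is left to exclude is marginal: an intermittent user, or perhaps someone who recently started a fixed dose.

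At stake is the reading of an individual ECG. If a beta blocker dose is still rising at Day 1, the baseline PR is taken on a moving background. A later PR rise could then come from the background drug, from ASN51, or from both. That could contribute to an interruption or discontinuation decision under Section 7.1.1, or make a first-degree AV-block event hard to attribute.

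**Working it through.** **Step 1: what the criterion excludes.** Set the two criteria side by side.

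| | Exclusion 33 | Exclusion 35 |
|---|---|---|
| Drugs | Acetylcholinesterase inhibitors, memantine | PR- or QT-prolonging drugs |
| Window | 8 weeks | 12 weeks |
| Dose change inside the window | Excluded | Exempt if titrating |
| Unchanged dose | Eligible | Eligible |

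The exempt set in exclusion 35 is (stable) or (titrating), which covers nearly all users. Exclusion 33 shows that the protocol already has wording that works.

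**Step 2: which drugs the gap concerns.** Exclusion 41 and Section 6.8.1 bar moderate and strong CYP3A4 inhibitors whether or not the dose is stable. The amendment summary reports that diltiazem, verapamil and dronedarone were added to Appendix 16 as moderate inhibitors, so the titration allowance cannot readmit them. What remains is beta blockers, other calcium channel blockers and other PR/QT-prolonging drugs.

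**Step 3: distance to the PR triggers.** Inputs are the two Section 7.1.1 criteria. For a baseline B in whole ms, the smallest PR that meets either criterion is the lower of:
- the smallest value in 200–220 ms that exceeds 1.10 × B;
- 221 ms.

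| Baseline (ms) | 1.10 × B | Smallest triggering PR (ms) | Rise (ms) | Rise (%) |
|---|---|---|---|---|
| 170 | 187.0 | 200 | 30 | 17.6 |
| 180 | 198.0 | 200 | 20 | 11.1 |
| 181 | 199.1 | 200 | 19 | 10.5 |
| 185 | 203.5 | 204 | 19 | 10.3 |
| 189 | 207.9 | 208 | 19 | 10.1 |
| 195 | 214.5 | 215 | 20 | 10.3 |
| 200 | 220.0 | 221 (second criterion) | 21 | 10.5 |

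Over baselines of 180 to 200 ms the rise needed is 19 to 21 ms. Further from the entry cap it grows: 30 ms from 170 ms.

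**Step 4: how a background change would enter.** The documents give no PR shift for any background drug. Purely as an assumption, suppose ongoing titration adds 5 to 15 ms after baseline. From 180 ms, ASN51 would then need to add 20 − 5 = 15 ms down to 20 − 15 = 5 ms to reach the trigger. From 170 ms it would need 30 − 5 = 25 ms down to 30 − 15 = 15 ms. This shows the mechanism and is not an estimate.

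**Step 5: QT.** Section 7.1.1 sets no numeric QTcF trigger after enrollment and leaves QTcF changes to judgement, so there is no matching arithmetic for QT.

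**Step 6: do other controls require a stable dose before baseline?**
- The PR cap tests a level at Screening. Screening may last up to 8 weeks, and no numeric PR limit is stated for Day 1.
- Table 2 schedules a second pre-dose triplicate ECG on Day 1, so a shift between the two would be visible. That detects movement but does not prevent entry.
- Section 6.8.2 asks for stable doses during the trial, mainly of drugs that affect cognition. It records prior medication for 30 days before Day 1, against a 12-week (84-day) window.
- Exclusions 20, 21 and 36 rest on judgement, and exclusion 35 expressly allows titration.

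None of these secures a stable dose.

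**The case against.** The strongest case on the other side is that the gap is small and well covered. Three relevant drugs are already barred. Exclusion 16 removes recent clinically significant conduction abnormalities. There are two pre-dose triplicate ECGs, serial ECGs afterwards, and dated medication records. Section 5.2 strongly encourages discussing eligibility questions with the Medical Monitor. Reaching a PR criterion starts a decision and does not force one. Safety p-values are descriptive. The bracketed words may be a slip for the opposite meaning, or a deliberate choice in favor of enrollment whose rationale lies in text missing from the public copy.

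Most of this stands, and it limits the consequence to individual attribution. It does not change what the criterion permits. If it is a slip, it is in an operative eligibility rule, and Sections 5.2 and 5.6 allow no waivers.

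Two stronger readings are tempting and should not be drawn.
- A reader might infer that the safety comparison is biased. Randomization with a concurrent placebo group gives no reason to expect systematic between-arm bias.
- A reader might infer that background titration threatens the Section 7.4 rule, which is met when "Two or more participants in a group show a 2nd degree AV block" or a higher-grade block, without comparison to placebo. That rule does not count PR prolongation or first-degree block. Nothing in the documents ties background titration to second-degree block in people screened at PR of 200 ms or less, and the rule convenes a review rather than stopping the trial. The link is at most a remote possibility.

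**Conclusion.** The point holds in a limited form and is a cheap improvement. As written, exclusion 35 does not secure a stable dose of a PR- or QT-prolonging drug before the baseline ECG, and nothing in the supplied text corrects it. In a participant who enters while titrating, a background dose change could supply part of the 19 to 21 ms (baseline 180 to 200 ms) or 30 ms (baseline 170 ms) that meets a Section 7.1.1 PR criterion, and could make that event hard to attribute.

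The size of the effect cannot be estimated. The documents give neither the number of participants likely to be titrating, nor the PR shift a background drug would cause, nor the distribution of baseline PR. The conclusion rests on sites applying the criterion literally and on Appendix 16 being as the amendment summary describes it.

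**What to change.** Delete the bracketed titration allowance and reword exclusion 35 on the pattern of exclusion 33: exclude anyone who started, or changed the dose of, a PR- or QT-prolonging drug within 12 weeks before randomization. Users on an unchanged dose stay eligible. Optionally, ask for a 12-week dose history of these drugs at the eligibility review, because the prior-medication record covers only 30 days.

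The change governs entry only. Medically necessary starts or dose changes after randomization stay allowed under Sections 6.8 and 6.8.2 and are recorded with dose and dates.

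The cost is a one-line amendment. A few candidates would wait until they had been on an unchanged dose for 12 weeks, or would fail screening.
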